7.8.7.10 Withdrawal, Missed Visit, and Loss to follow-up

The Investigator will make every attempt to follow the patients at each of the required assessment periods. Patients may be withdrawn from the study for the following:

- **Patient Withdrawal**

The patient may voluntarily withdraw from the clinical study at any time, without penalty or loss of benefits to which they are otherwise entitled.

- **Physician Withdrawal**

The Principal Investigator also has the right to withdraw a patient if they feel it is in the best interest of the patient to do so.

- **Missed Visit / Lost to Follow-up**

If a patient cannot be reached for a follow-up visit, the Investigator will document the contact efforts made to the patient and/or effort to obtain hospital records in the appropriate electronic case report form. If the patient cannot be reached in any way, or misses a visit, the patient will be considered "missed visit" for that time interval. After two

documented unsuccessful attempts to schedule follow up visits sequentially (e.g., 1 year and 2 year follow-up), the patient will be considered “lost to follow-up.”

In all cases of withdrawal (as described above), withdrawn patients will not undergo further study follow-up procedures after the time of study exit. A study patient that has been withdrawn from the study will not be replaced.

7.8.7.11 Patient Study Completion

Study patients complete and exit the study when no additional follow-up visits, procedures, or data collection are required. Patients may then continue to be followed by their primary health care provider as required.

A patient will also be exited from the study in the following instances:

- Patient signs informed consent form, is deemed eligible and considered provisionally enrolled but does not undergo the study procedure
- Patient undergoes study procedure and does not receive investigational device (will exit study at the 30 day follow up visit)
- Patient undergoes study device explant or removal (will exit study 30 days post-explant or removal)
- Patient withdraws participation from the study or is withdrawn from the study
- Patient is lost-to-follow-up
- Patient expiration

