7 CLINICAL INVESTIGATION

7.1 Study Design

This is a multi-center (up to 20 sites initially), multi-national, prospective, single arm study. The analysis population will consist of 60 patients. No site will be allowed to enroll more than 20% of the analysis population in the primary cohort. All enrolled study patients will be assessed for clinical follow-up at the following intervals: 30 days, 6 months, 1 year and annually for 5 years post implant procedure. In addition, the study allows for 0 to 3 roll-in patients per site where allowed, for a total maximum of 60 roll-in patients. The overall study therefore allows for up to 120 patients: 60 in the analysis population, and up to 60 additional roll-in patients.

Following completion of the primary cohort of 60 patients in the analysis population (up to 45 of which may be US patients), an additional 50 patients will be enrolled in the U.S. at up to 15 clinical sites.

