7.8.7.8 Follow Up Visits

Follow-up visits will be conducted at 1 month, 6 months, and annually for 5 years post implant.

The following procedures will be conducted during follow up visits:

- Clinical Evaluation (includes vital signs, weight and height), concomitant medication and NYHA classification
- Administration of Health Status Questionnaires at 1 month, 6 months and 1 year
- Administration of 6MWT at 1 month, 6 months and 1 year
- Safety Evaluation
- NIH stroke scale/Modified Rankin Scale*
- Clinical Laboratory Tests (troponin (if applicable), CK-MB (if applicable), BNP or NT-pro-BNP, CBC and platelets, complete metabolic panel, serum creatinine, PTT or PT/INR)
- Standard 12-lead ECG
- Comprehensive TTE
- MRI (optional, as deemed appropriate by Investigator).

Post-procedure follow up visits will be performed on all implanted study patients at 1 month, 6 months, and annually for 5 years post implant procedure intervals as summarized in Table 7.

* Modified Rankin Scale (mRS) will be conducted at baseline for all patients with a history of stroke and at each follow visit for all patient who had a stroke at any time period during the trial. The assessment should be done closest to 90 days post event.

Table 7: Follow-Up Visit Windows

Scheduled Follow-up Interval	Follow-up Window
1 month (30 days)	± 7 days
6 months (180 days)	± 30 days
Annually up to 5 years	± 45 days

During the follow up visits, medical information and assessment results will be entered in the appropriate CRFs.

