9.2 Analysis Population

- **Intent-to-treat population**

The intention-to-treat (ITT) population includes all patients in whom the study procedure has been attempted (i.e., incision).

- **Per-protocol population**

The per-protocol (PP) population includes all patients in whom the study device was introduced in the body, and do not have any major protocol deviations.

- **Roll-in population**

Up to three roll-in patients per site may be allowed, but not required (e.g., for sites with sufficient prior experience with the system). The study Sponsor will review each situation to determine when a site may start enrolling in the ITT population.

The PP population will be the primary analysis population for performance and safety assessment. The ITT population will be used for additional safety analysis. Subgroup analysis by etiology may be performed. For patients with mixed etiology, the echo core lab will determine the dominant etiology for analysis.

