#### 4. ANALYSIS POPULATIONS

- **Intent-to-treat population**

The intention-to-treat (ITT) population includes all patients in whom the study procedure has been attempted (i.e., incision). The ITT population does not include roll-in patients.

- **Per-protocol population**

The per-protocol (PP) population includes all patients in the ITT population in whom the study device was introduced in the body, and do not have any major protocol deviations.

- **Implanted population**

The implanted population includes all patients in whom the study device was implanted in the body at the time of the patient's exit from the cardiac catheterization laboratory.

- **Roll-in population**

Up to three roll-in patients per site may be allowed, but not required (e.g., for sites with sufficient prior experience with the system). The study Sponsor will review each situation to determine when a site may start enrolling in the ITT population.

The PP population will be the primary analysis population for performance and safety assessment. The ITT population will be used for additional safety analysis. Additional analyses of performance and safety data using the implanted population will be performed if it is clinically meaningful in addition to the PP analysis. Subgroup analysis by etiology may be performed. For patients with mixed etiology, the echo core lab will determine the dominant etiology for analysis. All analyses will be performed separately for the roll-in population.

A first analysis will be performed when 30 patients complete 30-day follow-up, and a second analysis when all patients complete their 30-day follow-up.

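### Patients who leave without the device, or have it explanted, exit early although they belong to analysis sets reported to 5 years, and the SAP does not say how they are then counted

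*Protocol*

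**What the plan says.** **Exit rules.** Protocol 7.8.7.11 lists two exits tied to the device: "Patient undergoes study procedure and does not receive investigational device (will exit study at the 30 day follow up visit" and "Patient undergoes study device explant or removal (will exit study 30 days post-explant or removal".

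**Follow-up.** Protocol 7.1, repeated in SAP 2.2, states: "All enrolled study patients will be assessed for clinical follow-up at the following intervals: 30 days, 6 months, 1 year and annually for 5 years". Protocol 7.8.7.8 is narrower: "Post-procedure follow up visits will be performed on all implanted study patients at 1 month, 6 months, and annually for 5 years".

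**Analysis sets.** In SAP section 4 the ITT set "includes all patients in whom the study procedure has been attempted (i.e., incision". The PP set, which is primary for safety and performance, "includes all patients in the ITT population in whom the study device was introduced in the body", provided there is no major deviation. Protocol 9.2 agrees. Neither set requires that a device be left in place, and neither removes a patient explanted later. The SAP defines a separate implanted population for that purpose.

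**Endpoints and methods.** Protocol 7.6 carries all-cause mortality, heart failure hospitalization and MAE forward annually. The SAP uses:
- Kaplan-Meier for mortality, Poisson regression for recurrent heart failure hospitalization, and counts and percentages for later MAE and re-intervention (6.4);
- linearized rates for late adverse events (6.3);
- censoring at the last known event-free point or last information date (5.1.3, 6.1c);
- denominators that in general contain only subjects with evaluable data (6.1b).

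Adverse event capture stops when participation ends (Protocol 8.1). Protocol 9.4 and SAP 6.2 provide neither vital status after exit nor a sensitivity analysis for these exits.

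**The concern.** The ITT and PP sets are deliberately wider than the implanted set. They are meant to show what happens to patients in whom the procedure or device was tried, including those in whom it failed. The exit rules largely undo that. A patient who leaves without a device contributes nothing after the 30-day visit, and an explanted patient contributes nothing beyond 30 days after explant. From then on the wider sets are followed in much the same patients as the implanted set, while keeping the ITT and PP labels.

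Kaplan-Meier assumes that censored patients have the same later risk as those still followed. Here censoring is triggered by the outcome of treatment, so the assumption needs support, and the plan gives none.

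The clearest case needs no view on prognosis. FDA Device Success (SAP 6.6) is reported at 30 days and at every later interval, and requires the original device to be in place. Exiters without it are failures by definition. With no later visit they may be treated as not evaluable and removed from the denominator. The FDA 1-year individual patient success measure is built on the same definition and inherits the question.

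One study objective is to guide future trial designs, and long-term rates from this cohort would be used that way.

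**Working it through.** The plan gives no non-implant, explant or dropout rate and no long-term mortality assumption, so there is no planned figure to reproduce. The check has three parts.

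**1. Who is affected, and where**

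| Patient | Set | Follow-up ends | Consequence |
|---|---|---|---|
| Procedure attempted, device never introduced | ITT only | 30-day visit | Later outcomes lost |
| Device introduced, none left in place | ITT; PP if no major deviation | 30-day visit | Later outcomes lost |
| Implanted, later explanted | ITT; PP if no major deviation | 30 days after explant | Earlier follow-up kept, later outcomes lost |

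Events before exit are captured. After exit, mortality is censored. Late linearized rates gain no person-time, and neither does the Poisson rate if follow-up time is the exposure (the SAP does not state the offset). Percentages may lose the patient from the denominator.

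**2. Size for mortality (illustration)**

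From the documents: N = 60 (Protocol 7.1) and a 5% annual death rate in symptomatic severe MR (Protocol 3.3). Assumed: k = 3 or 6 exiters, all leaving at day 30, with mortality hazard ratio HR = 1, 2 or 4 against the others.

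- Hazard λ = −ln(0.95) = 0.0513 per year; p = k/60; t₀ = 30/365 = 0.0822 years.
- Survival of all 60: S(t) = (1−p)·exp(−λt) + p·exp(−HR·λt).
- Large-sample Kaplan-Meier with exiters censored at t₀: S(t₀)·exp(−λ(t−t₀)).

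For k = 6, HR = 4, t = 5: S(5) = 0.9 × 0.7738 + 0.1 × 0.3585 = 0.7323, so mortality is 26.8%. Kaplan-Meier survival is 0.9945 × 0.7771 = 0.7728, so reported mortality is 22.7%. The difference is 4.1 points.

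| k | HR | 1 y, all 60 | 1 y, KM | Gap | 5 y, all 60 | 5 y, KM | Gap |
|---|---|---|---|---|---|---|---|
| 3 | 2 | 5.2% | 5.0% | 0.2 | 23.5% | 22.6% | 0.9 |
| 3 | 4 | 5.7% | 5.1% | 0.6 | 24.7% | 22.7% | 2.0 |
| 6 | 2 | 5.5% | 5.0% | 0.4 | 24.4% | 22.7% | 1.7 |
| 6 | 4 | 6.4% | 5.1% | 1.2 | 26.8% | 22.7% | 4.1 |

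Gaps are taken before rounding. With HR = 1 the gap is zero. If exiters' deaths before day 30 were also left out, the largest 1-year gap would be 6.36 − 5.00 = 1.36, about 1.4 points. The exit rule keeps those deaths, so 1.2 is the matching figure.

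Bounds that need no hazard ratio, with 22.6% 5-year mortality in the patients retained:
- k = 6: from 54 × 0.226/60 = 20.4% (no exiter dies) to (54 × 0.226 + 6)/60 = 30.4% (all die).
- k = 3: 21.5% to 26.5% in the same way.

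**3. Size for FDA Device Success**

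Dropping k known failures multiplies the success rate by 60/(60−k): 60/57 = 1.05 for k = 3 and 60/54 = 1.11 for k = 6. If 80% of those remaining succeed (assumed), the rate in all 60 is 0.80 × 57/60 = 76% or 0.80 × 54/60 = 72%.

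**The case against.** **Long-term results will look too good.** A reader might infer this, but the documents do not establish it. Every patient must be a surgical candidate (inclusion criterion 4), so some exiters may go to surgery. In the randomized comparison of another edge-to-edge device with surgery (Protocol 3.4.3.3), mortality was similar (6% in both arms at 1 year; 20.8% against 26.8% at 5 years, p = 0.36), and surgery reduced MR more. Equal prognosis gives no bias, and better prognosis in exiters reverses the sign. This stands.

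**The loss is large.** That would need very high mortality in exiters, for which the documents give no source. Late explants also contribute all their earlier follow-up, so the day-30 model overstates their effect. For scale, the exact 95% interval around 7 deaths in 60 is 4.8% to 22.6%, far wider than the illustrated 1-year gap. This stands as a limit on size. Sampling error is, however, visible in the report, and this bias would not be.

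**Device failures vanish from the event analyses.** They do so only in part. An explant for a device complication is probably already an MAE through re-intervention. SAP 6.1b applies in general and does not say that a patient with a recorded event is removed. The supportable statement is that the counting rule is unspecified.

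**Section 7.1 is flatly contradicted.** The conflict is partial. Section 7.8.7.8 already limits visits to implanted patients, which fits the non-implant exit. It does not fit the explant exit, since an explanted patient was implanted.

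**The affected outcomes are secondary and descriptive.** This is correct. All primary endpoints fall at or before 30 days.

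**Conclusion.** The point holds as a risk of informative censoring and an unspecified counting rule. It is not a demonstrated bias in a known direction. Patients who belong to the ITT and, in most of these cases, PP sets stop being followed because the device was not placed or was removed. No other provision recovers their later outcomes.

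The mortality understatement of 0.2 to 1.2 points at 1 year and 0.9 to 4.1 points at 5 years rests on 5% annual mortality, 3 to 6 exiters at day 30, and a hazard ratio of 2 to 4. Only the 5% comes from the protocol. The FDA success calculation makes no assumption about prognosis, but depends on how many patients exit and on whether SAP 6.1b is applied to them.

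A reader might conclude that the 30-day primary safety endpoint is compromised. It is largely unaffected, because exits occur at the 30-day visit or 30 days after explant. This is a change worth making for the long-term results, and it does not undermine the primary analysis.

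**What to change.** 1. Amend Protocol 7.8.7.11 so that every patient with an attempted procedure is followed, subject to consent, for vital status, hospitalization and MAE by telephone or record review at the scheduled times to 5 years. Device-specific echocardiography may stop.
2. State in SAP 6.6 that patients without the original device count as failures, and stay in the denominator, for FDA Device Success at every later interval and for FDA Individual Patient Success.
3. State in SAP 6.1b and 6.4 how exiters are counted in the MAE and re-intervention percentages, and name the exposure time for the Poisson model.
4. Add a bounding sensitivity analysis for any remaining exits (none die, all die) beside the Kaplan-Meier mortality estimates, and report the number and timing of exits by reason.
5. Reconcile Protocol 7.1 and SAP 2.2 with Protocol 7.8.7.8 and 7.8.7.11.

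The cost is an amendment and a few contacts per year for what is likely to be a handful of patients. The long-term rates may come out slightly less favourable. Outcomes not collected at the time may be hard to recover later.

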8 ADVERSE EVENTS, ADVERSE DEVICE EFFECTS AND DEVICE DEFICIENCIES

8.1 Reporting Procedure

Adverse events will be captured from the time of enrollment (after patient eligibility is confirmed, per section 7.8.3) until the study patient's participation has ended (i.e. completion of study or withdrawal of consent).

The Investigator will report all adverse events to the Sponsor as soon as possible, but no later than 10 working days after the Investigator first learns of the event (but no later than 3 calendar days after awareness for patients at EU sites)

Each adverse event must be reported on a separate AE CRF. In the event that the EDC system is not in service or is otherwise not accessible, the Sponsor must be notified by email

[REDACTED] The AE CRF should be completed as soon as possible thereafter.

At the time of initial notification, the following minimal information must be provided:

- Study site number
- Patient ID number
- Date of event
- Site's awareness date
- AE description
- Causal relationship to device and implant procedure, if known

The site will provide the Sponsor or designee copies of relevant supporting source documentation (e.g. admission H&P, implant procedure report, discharge summary, echocardiogram and laboratory results) for all adverse events requiring CEC adjudication (at a minimum, safety endpoints) and those events determined by the Sponsor to require additional investigation.

Study patients will be carefully monitored during the clinical study for any possible adverse event. All adverse events will be fully investigated by the Investigator. Appropriate treatment for the patient will be initiated while the study follow up continues. Adverse events must be followed

until resolution, the patient is lost to follow-up, the patient has withdrawn consent, or the adverse event is otherwise explained.

The Investigator will attempt to assess the involvement of the investigational device and / or study procedure in the adverse event. All observations and clinical findings, including the nature or the severity, will be documented on the appropriate case report form.

The Investigator will report all adverse events to their local Institutional Review Board/Ethical Committee and / or National Regulatory Agency in accordance with the applicable requirements.

8.1.1 Findings that do not require reporting to the sponsor:

For purposes of this study, the following findings are not considered adverse events requiring reporting to the Sponsor. These findings are normally expected to occur in association with treatment of mitral regurgitation or interventional structural heart procedures, or are associated with customary, standard care of patients undergoing transcatheter cardiovascular intervention:

- Post-operative pain (within 48 hour of procedure) not requiring treatment or treated with non-opioids
- Post-anesthesia emesis, nausea, or headache (within 24 hours of procedure).
- Abnormal or out of range lab values (e.g. electrolyte imbalance) that are not clinically significant and do not require correction or treatment.

Note: Abnormal lab values that roll up to a diagnosis should not be reported as separate AEs (e.g. elevated BNP in patient with heart failure; increased K⁺ in patient with renal insufficiency; elevated WBC in patient with infection)

- Pre-planned future surgical procedures not associated with the study procedure or device.
- Low grade temperature increase ($\leq 101^{\circ}\text{F}$ or 38.5°C) without signs or symptoms of infection.
- Minor, localized tenderness, swelling, induration, oozing, etc. at access site(s).
- Sinus bradycardia or tachycardia that does not require treatment or intervention
- Systolic or diastolic blood pressure changes that do not require treatment or intervention.
- Expected, non-clinically significant events such as non-clinically significant lab variances that do not require treatment.

This listing of findings is intended to provide guidance to the investigational sites for the purpose of adverse event reporting. The Investigator should utilize his/her own clinical judgment in evaluating adverse experiences, and may decide that the above findings should be reported as adverse events.

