6.2 Risk Management

All efforts will be made to minimize the identified risks. Careful patient selection will be performed by the Heart Team¹¹ in collaboration with the Sponsor.

The Investigators selected at each site will include an Interventional Cardiologist or Surgeon who is an expert in mitral valve disease and experienced in performing transcatheter mitral valve repair and/or replacement, and skilled in percutaneous coronary interventions and structural heart interventions to assess patient risk and anatomical suitability. Each implanting physician will be thoroughly trained on the investigational device before first implantation in a patient. There will be strong collaboration between interventional cardiology or cardiac surgery and a designated team of nurses, technicians and colleagues from supporting medical disciplines (e.g., anesthesiologist, echocardiographer, and radiologist).

The procedure will be performed in an operating room, catheterization lab or hybrid operating room with fluoroscopic and echocardiographic imaging capabilities.

All adverse events will be thoroughly monitored and reviewed by the Study Sponsor and DSMB. Stopping rules will be applied for patient safety throughout enrollment.

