8.3 Deaths and Explants

8.3.1 Patient Deaths

In the event of patient death, every effort should be made to obtain a copy of the autopsy report and/or death summary. Information on the cause of death and its relationship to the investigational device or study procedure will be determined by the Investigator. Copies of an autopsy report, if available, and/or a death summary are to be forwarded to the Study Sponsor. If a device is explanted during autopsy, the device should be returned to the Study Sponsor for analysis. Return kits for devices will be provided upon request by the clinical monitor.

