11 DEVIATIONS FROM CLINICAL INVESTIGATION PLAN

11.1 Protocol Deviation

If an Investigator or designee contacts a Clinical Affairs representative to obtain prior approval for a change to the clinical study requirements, the approval or disapproval will be documented in writing. A copy of the approval or disapproval will be forwarded to the Investigator and a copy will be maintained in the study files.

A major protocol deviation or noncompliance are those that may have a significant impact on subject safety, well-being, the subject's willingness to participate in the study, or that may compromise the integrity of the study data and analysis, including:

- a) Subject implanted/treated with study device not having met eligibility criteria at the time of implant/treatment.
- b) Informed Consent not signed or signed after the initiation of non-standard of care, research related assessments.
- c) UADE not reported to IRB/EC/Sponsor within the required timeframe
- d) Unauthorized use/implant of an investigational device

A minor protocol deviation or noncompliance is unlikely to have a significant impact on subject safety, wellbeing, or is unlikely to compromise the integrity of the study data and analysis. All protocol deviations or noncompliances will be reported to the IRB/EC, as required.

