13.1.3 Investigator Reports

The Investigator will prepare and submit the following accurate and complete reports to the Study Sponsor and IRB/EC in a timely manner:

Anticipated and unanticipated serious adverse device effects occurring during the study will be reported as described in section 8.1.

Withdrawal of IRB/EC approval will be reported to the Sponsor within 5 working days

Annual progress reports will be submitted to the IRB/EC.

Deviation from the clinical study protocol. Deviations to protect the patient's life or physical well-being in an emergency will be reported to the Study Sponsor within 5 working days and to the IRB/EC according to their reporting policy.

Use of the study device without informed consent will be reported within 5 working days after the use occurs.

A final written report within three months of completion or termination of the trial.

Upon request by a reviewing IRB/EC or the pertinent regulatory agencies, the Principal Investigator will provide current information about any aspect of the investigation.

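### Protocol 8.1 gives non-EU sites no shorter sponsor-notification limit for serious, fatal or unanticipated device events: the only ceiling is 10 working days, against 3 calendar days at EU sites

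*Protocol*

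**What the plan says.** Protocol Section 8.1 states the general rule: "The Investigator will report all adverse events to the Sponsor as soon as possible, but no later than 10 working days" after first learning of the event. The same sentence carries a regional exception: "no later than 10 working days after the Investigator first learns of the event (but no later than 3 calendar days after awareness" for EU sites). Both limits cover adverse events of every kind, and seriousness does not change the clock.

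Four other sections bear on timing, and none of them shortens it for serious events:

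- **Section 13.1.3** says: "Anticipated and unanticipated serious adverse device effects occurring during the study will be reported as described in section 8.1". The same section gives 5 working days for withdrawal of IRB/EC approval, for emergency deviations made to protect a patient, and for use of the device without consent.
- **Section 8.3.1**, on deaths, says: "Copies of an autopsy report, if available, and/or a death summary are to be forwarded to the Study Sponsor". It gives no number of days.
- **Section 11.1** lists as a major deviation "UADE not reported to IRB/EC/Sponsor within the required timeframe", without saying what that timeframe is.
- **Section 8.2.9**, on device deficiencies, requires documentation on the eCRF and gives no day limit for any region.

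On oversight, Section 6.2 says: "Stopping rules will be applied for patient safety throughout enrollment". Section 10.1.1 has the DSMB review aggregate safety data on an ongoing basis. On enrolment, Section 7.1 allows up to 45 US patients among the 60 in the primary cohort, after which "an additional 50 patients will be enrolled in the U.S. at up to 15 clinical sites".

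**The concern.** This is an investigational implant, and patients continue to be treated while safety information accumulates. The sponsor's classification of each event (Section 8.2.8), the stopping rules (6.2), the DSMB's review (10.1.1) and the power to suspend (12.5) all depend on the sponsor having received the report. At non-EU sites the latest date for a fatal stroke is the same as for a trivial event.

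The protocol's own ordering makes this look unintended. A withdrawn ethics approval must reach the sponsor within 5 working days, while a death or an unanticipated device effect at a US site is allowed 10. EU sites in the same trial report everything within 3 calendar days, so a shorter limit is already being operated. At stake is how long a serious event after the procedure, including a component of the 30-day MAE endpoint, may remain unknown to the sponsor during open enrolment.

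**Working it through.** The plan gives no figure of its own to reproduce. The check has three parts: convert the limits to a common unit, size the group they apply to, and look for any passage that overrides them.

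**1. Length of the limits (Section 8.1).** Ten working days on a Monday-to-Friday calendar, counted from the day of awareness, less the 3-day EU limit:

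| Day of awareness | 10 working days, in calendar days | Excess over 3 days |
|---|---|---|
| Monday to Friday | 14 | 14 − 3 = 11 |
| Saturday | 13 | 13 − 3 = 10 |
| Sunday | 12 | 12 − 3 = 9 |

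One public holiday in the window lengthens it to 15 to 17 calendar days. Without holidays the excess is 9 to 11 days.

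**2. Patients under the longer limit (Section 7.1).** Write k for the number of US patients in the primary cohort, from 0 to 45.

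- Largest US share of the primary cohort: 45/60 = 75%.
- US share of both cohorts together: (k + 50)/(60 + 50).
  - k = 0: 50/110 = 45%.
  - k = 6: 56/110 = 51%, the first value above half.
  - k = 45: 95/110 = 86%.
- If all 60 permitted roll-in patients are enrolled, the extremes are 50/170 = 29% (no US patients in the primary cohort and none among the roll-ins) and (45 + 50 + 60)/170 = 155/170 = 91% (45 in the primary cohort and every roll-in from the US).

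SAP Section 2.2 plans 45 US patients, but it lets the US group go on enrolling after the 60-patient cohort fills, so it does not fix k at 45. SAP Section 6.5 also names Canada. The US share is therefore a lower bound on the non-EU share for any given k.

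**3. Search for an override.** Serious adverse device effects are sent back to 8.1 by Section 13.1.3. Other serious events fall under 8.1 directly, because it covers all adverse events. Sections 8.3.1 and 11.1 contain no number. The only other numbers for notices to the sponsor are the 5-working-day items in 13.1.3, and these do not cover adverse events. On the protocol's own scale, 10/5 = 2: a serious event at a non-EU site is allowed twice the time of those notices.

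**The case against.** The best defence is that 10 working days is a ceiling attached to an instruction to report promptly. A report inside that window is on time, and the documents contain no actual reporting times. Other safeguards exist. Monitoring visits check that reports to the sponsor are timely (10.3.1), late reporting of an unanticipated device effect is a major deviation (11.1), and investigators report separately to ethics committees and national agencies (8.1). A trained sponsor representative attends every implant (7.8.7.4), so many intraprocedural events may be known at once. The two regional limits are stated openly and do not contradict each other, and they may follow regional rules that are not in the documents.

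Most of this stands, and it limits the point. It does not remove it: none of these provisions sets a shorter time to the sponsor for a serious event after the patient leaves the procedure room, and a regional legal maximum would not prevent a shorter protocol limit.

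A reader might go further in three ways that the documents do not support:

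- **That safety oversight lags by two weeks.** Fourteen days is the longest permitted interval from site to sponsor, and the excess over EU sites is 9 to 11 days. The DSMB's meeting interval, the stopping thresholds and the enrolment rate are not given. Neither the effect on a DSMB decision nor the number of patients treated meanwhile can be derived.
- **That data snapshots under-count US events.** The planned analyses are triggered by completed 30-day follow-up (9.3), and data are queried before use (10.4). Only events learned of just before a snapshot and reported near the limit could be missed. No bias is shown.
- **That most of the trial is certainly affected.** This is likely, but 45 is a cap and the region of the roll-ins is unknown.

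**Conclusion.** The point holds as a design weakness, not as an inconsistency. Section 8.1 has no separate, shorter sponsor-notification limit for serious, fatal or unanticipated device events at non-EU sites. The permitted maximum there is about 14 calendar days against 3 at EU sites, an excess of 9 to 11 days. It bears mainly on events after the implant procedure.

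Up to 95 of 110 patients (86%) may fall under the longer limit through US enrolment alone. That figure assumes the full 45 US patients in the primary cohort and leaves out roll-ins and any other non-EU sites. The day counts assume a Monday-to-Friday week without public holidays. The conclusion does not depend on sites using the whole window. It rests on the protocol allowing them to, while giving less urgent notices half the time.

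**What to change.** In Section 8.1, apply the existing 3-calendar-day limit at all sites to serious adverse events, deaths, and serious or unanticipated adverse device effects. Keep 10 working days for non-serious events outside the EU. Refer to the new limit in Section 13.1.3, and use it to define the timeframe for reporting to the sponsor that Section 11.1 leaves without a number.

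Device deficiencies are not part of this change. The EU limit covers adverse events only, so a day limit for deficiencies would be a new obligation at every site, including EU sites.

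The cost is protocol wording, retraining, and faster data entry for serious events at non-EU sites. EU sites already meet the limit for these events. One side effect should be settled when Section 11.1 is edited: a late report of an unanticipated device effect is a major deviation, and Section 9.2 removes patients with major deviations from the per-protocol population, which is primary for safety. The sponsor should say whether lateness of a report alone is meant to exclude a patient.
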